6.2 Preparation, handling, storage, and accountability

Each study site will be supplied with study treatment in packaging as described under Section 6.1.

A unique medication number is printed on the study medication label.

Investigator staff will identify the study medication kits to dispense to the participant by contacting the IRT and obtaining the medication number(s). The study medication has a 2-part label (base plus tear-off label), immediately before dispensing the medication kit to the participant, site personnel will detach the outer part of the label from the packaging and affix it to the source document.

As per Section 4.5, during a public health emergency as declared by local or regional authorities i.e. pandemic, epidemic or natural disaster, that limits or prevents on-site study visits, delivery of IMP directly to a participant's home may be permitted (if allowed by local or regional health authorities and ethics committees as appropriate) in the event the Investigator has decided that an on-site visit by the participant is no longer appropriate or possible, and that it is in the interest of the participant's health to administer the study treatment even without performing an on-site visit. The dispatch of IMP from the site to the participant's home remains under the accountability of the Investigator. Each shipment/provisioning will be for a maximum of 3 cycles supply. In this case, regular phone calls or virtual contacts (every 3 weeks minimum, or more frequently if needed) will occur between the site and the participant for instructional purposes, safety monitoring, investigation of any adverse events, ensuring participants continue to benefit from treatment, and discussion of the participant's health status until the participants can resume visits at the study site.

6.2.1 Handling of study treatment

Study treatment must be received by a designated person at the study site, handled and stored safely and properly and kept in a secured location to which only the Investigator and designated site personnel have access. Upon receipt, all study treatment must be stored according to the instructions specified on the JDQ443 bottle label.

Clinical supplies are to be dispensed only in accordance with the protocol. Technical complaints are to be reported to the respective Novartis Country Organization Quality Assurance.

Medication labels will be in the local language and comply with the legal requirements of each country. They will include storage conditions for the study treatment but no information about the participant except for the medication number.

The Investigator or designated site staff must maintain an accurate record of the shipment and dispensing of study treatment in a drug accountability log. Monitoring of drug accountability will be performed by field monitors during site or remote monitoring visits, and at the completion of the trial.

Participants will be asked to return all unused study treatment and packaging at the end of the study or at the time of discontinuation of study treatment.

The site may destroy and document destruction of unused study treatment, drug labels and packaging, as appropriate in compliance with site processes, monitoring processes, and per local

regulation/guidelines. Otherwise, the Investigator will return all unused study treatment, packaging, drug labels, and a copy of the completed drug accountability log to the Novartis monitor or to the Novartis address provided in the Investigator folder at each site.

6.2.2 Handling of other treatment

Not Applicable

6.2.3 Instruction for prescribing and taking study treatment

All dosages prescribed and dispensed to participants and all dose changes during the study must be recorded on the Dose Administration Record eCRF. Doses and treatment schedules are described in Table 6-2.

Table 6-2 Dose and treatment schedule

Investigational Drug (Name and Strength)	Dose	Frequency and/or Regimen
JDQ443 (100 mg)	200 mg (2 x 100 mg)	Twice a day (b.i.d)

JDQ443 will be administered orally as a flat-fixed dose.

A sufficient supply of JDQ443 should be provided to participants to allow study treatment selfadministration at home until at least the next study visit at the clinic. At subsequent visits, site staff will provide additional bottles to ensure the study treatment supply until discontinuation of study treatment.

Participants should take their dose at approximately the same time each day. The first daily dose should be taken in the morning and the second dose should be taken approximately 12 h after the first dose (e.g., 08:00 and 20:00). If a dose is not taken within 4 h of the planned dosing time, the missed dose should not be replaced

JDQ443 should be administered with food. Participants should take JDQ443 immediately (within 30 minutes) following a meal.

Each dose of JDQ443 is to be taken with a glass of water and consumed over as short time as possible.

The tablets should be ingested whole and should not be chewed or crushed.

If vomiting occurs during the course of treatment, no re-dosing of the participant is allowed before the next scheduled dose. If the vomiting occurs on PK sampling days within the first 4 h post-dosing, this event should be recorded on the dose administration PK electronic eCRF page, as well as on the AE eCRF, as appropriate.

On days when PK blood samples are to be collected, participants will be instructed to hold their dose until arrival at the study center. JDQ443 will be administered with food at the site in the morning prior to the PK blood draws, except for pre-dose samples which will be collected immediately before JDQ443 administration. The administration will be supervised by a member of the research team. The dose, exact date and time of drug administration, exact date and time of PK blood draws, and meal record (start/end time) should be recorded in the appropriate eCRF.

The Investigator or responsible site personnel should instruct the participant to take the study treatment exactly as prescribed to promote compliance.

Participants should inform the investigational site staff of any missed or delayed doses.

All kits of study treatment assigned by the IRT will be recorded in the IRT system.

All dosages prescribed and dispensed to the participant and all dose changes during the study must be recorded on the Dosage Administration Record eCRF.

6.3 Measures to minimize bias: randomization and blinding

6.3.1 Treatment assignment, randomization

No randomization will be performed in this study. The assignment of a participant to a particular cohort will be driven by eligibility criteria and coordinated by Novartis. The response assessment for the study's primary endpoint according to RECST 1.1 will be performed by BIRC in order to mitigate the risk of bias.

6.3.2 Treatment blinding

Not Applicable

6.3.3 Emergency breaking of assigned treatment code

Not Applicable

6.4 Study treatment compliance

The date and time of study treatment administration during the study and any deviations from the protocol treatment schedule will be captured on the appropriate study treatment dispensation form.

The Investigator must promote compliance by instructing the participant to take the study treatment exactly as prescribed and by stating that compliance is necessary for the participant's safety and the validity of the study. The participant must also be instructed to contact the Investigator if he/she is unable for any reason to take the study treatment as prescribed.

For JDQ443, compliance will be assessed by the Investigator and/or study personnel at each visit using pill counts and information provided by the participant. This information should be captured in the source document at each visit. All study treatment dispensed and returned must be recorded in the Drug Accountability Log.

6.5 Dose modification

6.5.1 Dose modification guidelines

For participants who do not tolerate the protocol-specified dosing schedule, dose interruptions, and/or reductions are either recommended or mandated in order to allow participants to continue the study treatment.

These dose modifications for JDQ443 are summarized in Table 6-3 and Table 6-4. Deviations to mandatory dose interruptions and/or reductions are not allowed. Permanent discontinuation from study treatment is mandatory for specific events indicated as such in Table 6-3 and Table 6-4.

Dose reductions are allowed for JDQ443 and should follow the dose reduction steps described in Table 6-3 and Table 6-4. For each participant, a maximum of two consecutive dose level reductions is allowed after which the participant must be discontinued. Dose reductions of JDQ443 below 100 mg QD. are not permitted.

Dose re/escalation of JDQ443 to previous dose level is allowed only once, and if no AE leading to dose modification is observed after at least 1 cycle (21 days) of study treatment at the reduced dose.

For toxicities related to study treatment that resolve within 7 days of event onset, treatment may be resumed at the same or a lower dose level at the Investigator's discretion, except for toxicities that require permanent treatment discontinuation (Table 6-3 and Table 6-4).

For toxicities related to study treatment that result in dose interruptions of more than 7 but not more than 21 days, study treatment may be resumed but only at a lower dose level. If the participant is already at the lowest dose level, participant might continue receiving treatment at the same dose level if participant is deriving clinical benefit from JDQ443. In such situation, the Investigator must discuss and receive approval from Novartis Medical Monitor or designee prior to continuing JDQ443 and rationale should be captured in the source document.

If the participant requires a dose interruption of more than 21 days from the intended day of the next scheduled dose, then the participant must be discontinued from the study treatment. Exceptions to this criterion may be considered if the participant is deriving clinical benefit from the treatment. The Investigator must discuss and receive approval from Novartis Global Medical Director or designee prior to continuing study treatment in this situation and rationale should be captured in the source documents. If study treatment is reintroduced after an interruption of more than 21 days caused by an adverse event, study treatment can only be reintroduced at a lower dose level. If study treatment is reintroduced after an interruption of more than 21 days that was not caused by an adverse event, study treatment may be reintroduced without dose reduction.

All dose changes must be recorded on the appropriate eCRF.

Criteria for dose reduction / interruption and re-initiation of JDQ443 treatment for adverse drug reactions. Table 6-3

	reactions.
Dose modifications for JDQ443	
Worst toxicity	
CTCAE Grade ^a (value) during a cycle of therapy	
Investigations (Hematologic)	
Neutropenia (ANC)	
Grade 1 (ANC < lower limit of normal (LLN) - 1500/mm³)	Recommendation: Maintain study treatment and dose level.
Grade 2 (ANC < 1500 - 1000/mm ³)	Recommendation: Maintain study treatment and dose level.
Grade 3 (ANC < 1000 - 500/mm ³)	Recommendation: Interrupt study treatment until resolved to ≤ Grade 2, then:
	If resolved in ≤ 7 days, maintain dose level.
	If resolved in > 7 days, reduce 1 dose level.
Grade 4 (ANC < 500/mm³)	Mandatory: Interrupt study treatment until resolved to ≤ Grade 2, then reduce 1 dose level.
Thrombocytopenia	
Grade 1 (PLT < LLN - 75,000/mm ³)	Recommendation: Maintain study treatment and dose level.
Grade 2 (PLT < 75,000 - 50,000/mm ³)	Recommendation: Maintain study treatment and dose level.
Grade 3 (PLT < 50,000 - 25,000/mm ³)	Recommendation: Interrupt study treatment until resolved to ≤ Grade 2, then:
	If resolved in ≤ 7 days, maintain dose level.
	If resolved in > 7 days, reduce 1 dose level.
	Mandatory: For Grade 3 thrombocytopenia associated with major bleeding, permanently discontinue study treatment.
Grade 4 (PLT < 25,000/mm³)	Mandatory: Interrupt study treatment until resolved to ≤ Grade 2, then reduce 1 dose level.
	Mandatory: For Grade 4 thrombocytopenia associated with major bleeding, permanently discontinue study treatment.
Febrile neutropenia (ANC < 1.0×10^9 /L, with a single temperature of >38.3 degrees C [101 degrees F] or a sustained temperature of \geq 38 degrees C [100.4 degrees F] for more than one hour)	Mandatory: Interrupt study treatment until resolved, then reduce 1 dose level.
Anaemia	
Grade 1 (Hemoglobin [Hgb] < LLN - 10.0 g/dL; < LLN - 6.2 mmol/L; < LLN - 100 g/L)	Recommendation: Maintain study treatment and dose level.
Grade 2 (Hgb < 10.0 - 8.0 g/dL; < 6.2 - 4.9 mmol/L; < 100 - 80 g/L)	Recommendation: Maintain study treatment and dose level.
Grade 3 (Hgb < 8.0 g/dL; < 4.9 mmol/L; < 80 g/L; transfusion indicated)	Recommendation: Interrupt study treatment until resolved to ≤ grade 2, then:
	If resolved in ≤ 7 days, resume study treatment at the same dose level;
	If resolved in > 7 days, reduce 1 dose level.
Grade 4 (Life-threatening consequences; urgent intervention indicated)	Mandatory: Interrupt study treatment until resolved to ≤ grade 2, then reduce 1 dose level.

Investigations (Renal)	
Serum creatinine	
Grade 1 (> ULN - 1.5 × ULN)	Recommendation: Maintain study treatment and dose level.
Grade 2 (> 1.5 - 3.0 × ULN)	Recommendation: Interrupt study treatment and manage according to institutional practice.
	Upon resolution to ≤ Grade 1, may reintroduce study treatment at the same dose level if clinically indicated.
Grade 3 (> 3.0 - 6.0 × ULN) and Grade 4 (> 6.0 × ULN)	Mandatory: Permanently discontinue study treatment.
Investigations (Hepatic)	
Isolated total Bilirubin elevation	
Grade 1 (> ULN – 1.5 × ULN)	Recommendation: Maintain study treatment and dose level.
Grade 2 (> 1.5 - 3.0 × ULN)	Recommendation: Interrupt study treatment.
	Repeat LFTs ^b within 48-72 hours, then monitor LFTs at least weekly, until resolved to ≤ 1.5 × ULN or to baseline, then:
	• If resolved in ≤ 7 days, resume study treatment at the same dose level;
	If resolved in > 7 days, reduce 1 dose level.
Grade 3 (> 3.0 - 10.0 × ULN)*	Recommendation: Interrupt study treatment.
	Repeat LFTs ^b within 48-72 hours, then monitor LFTs at least weekly, until resolved to ≤ 1.5 × ULN or to baseline. May reintroduce study treatment at 1 lower dose level if clinically indicated.
Grade 4 (> 10.0 × ULN)*	Mandatory: Permanently discontinue study treatment.
	The participant should be monitored at least weekly (including LFTs ^b), or as clinically indicated, until total bilirubin has resolved to ≤ 1.5 × ULN or to baseline.

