	Repeat LFTs ^b as soon as possible, preferably within 48-72 hours from awareness of the abnormal results; monitor LFTs ^b at least weekly, until resolved to baseline or stabilization over 4 weeks.	
Combined ^c elevations of AST or ALT and total biliru	ıbin	
For participants with normal baseline ALT and AST and total bilirubin value:	Mandatory: Interrupt study treatment and adjudicate for DILI:	
AST or ALT >3.0 × ULN combined with total bilirubin > 2.0 × ULN without evidence of cholestasis ^d and Gilbert's syndrome For participants with elevated baseline AST or	Repeat as soon as possible, preferably within 48 hours from awareness of the abnormal results, monitor LFTs ^b at least weekly, or as clinically indicated, until AST, ALT, and total bilirubin have resolved ≤ Grade 1 or to baseline.	
ALT or total bilirubin value: AST or ALT > 3 × baseline OR > 8.0 × ULN.	If causality assessment indicates that DILI is	
whichever is lower, combined with total bilirubin > 2 ×	confirmed: Permanently discontinue study treatment.	
baseline AND > 2.0 × ULN Note: For participants with Gilbert's syndrome, at least 2-fold increase in direct bilirubin.	If not DILI: Treat the identified cause according to institutional guidelines. Once resolved to ≤ Grade 1 or to baseline, may reintroduce study treatment at 1 lower dose level if clinically indicated, following discussion with Novartis medical monitor.	
	Refer to Section 6.5.3.1 for further details on the follow up of potential drug-induced liver injury (DILI) cases.	
Investigation (metabolic)		
amylase and/or lipase elevation		
Grade 1 (> ULN - 1.5 × ULN)	Recommendation: Maintain study treatment and dose level.	
Grade 2 (> 1.5 - 2.0 × ULN)	Recommendation: Maintain study treatment and dose level.	

Grade 3 (> 2.0 - 5.0 × ULN) with signs or symptoms; > 5.0 × ULN and asymptomatic.**	Recommendation: Interrupt study treatment until resolved to Grade ≤ 1 or baseline, then:	
	If resolved in ≤ 7 days, resume study treatment at the same dose level.	
	If resolved in > 7 days, reduce 1 dose level.	
Grade 4 (> 5.0 × ULN with signs or symptoms)**	Mandatory: Permanently discontinue study treatment.	
Cardiac Investigations		
Left Ventricular Ejection Fraction (LVEF)		
LVEF < 40%	Mandatory: Interrupt study treatment, obtain consultation with cardiologist and repeat cardiac imaging after 3 weeks. If improved to > 45%, restart study treatment at the same dose. If not improved to >45%, permanently discontinue study treatment.	

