Fatigue/ Asthenia (General disorders and administ	ration site conditions)	
Grade 1 and 2	Recommendation: Maintain study treatment and dose level.	
Grade 3	Recommendation: Interrupt study treatment until resolved to ≤ grade 1, then:	
	If resolved in ≤ 7 days, maintain dose level.	
	If resolved in > 7 days, reduce 1 dose level.	
Ocular (uveitis, eye pain, blurred vision)		
Grade 1	Recommendation: Maintain study treatment and dose level. Ophthalmology consultation is required within 72 hours, except for dry eye.	
Grade 2	Recommendation: Interrupt study treatment.	
	Urgent ophthalmology consultation.	
	Upon resolution to ≤ Grade 1 in < 14 days, may consider reintroducing study treatment without dose reduction after discussion with the Novartis medical Monitor and consultation with ophthalmology.	
	Upon resolution to ≤ Grade 1 in ≥ 14 days, study treatment may be reintroduced at 1 lower dose level after discussion with the Novartis Medical Monitor and consultation with ophthalmology.	
Grade 3 and Grade 4	Mandatory: Permanently discontinue study treatment. Urgent ophthalmology consultation.	
Retinal vein occlusion or Retinal detachment		
Any Grade	Mandatory: Permanently discontinue study treatment. Urgent ophthalmology consultation.	
Other adverse events		
Grade 1 and 2	Recommendation: Maintain study treatment and dose level.	
Grade 3	Recommendation: Interrupt study treatment until resolved to ≤ grade 1, then reduce 1 dose level.	
	Mandatory: Interrupt study treatment for ≥ grade 3 vomiting or grade 3 nausea only if the vomiting or nausea cannot be controlled with optimal anti-emetic therapy (as per local practice).	
Grade 4	Mandatory: Permanently discontinue study treatment.	

^a Common Toxicity Criteria for Adverse Events (CTCAE Version 5.0)

^b Core LFTs consist of ALT, AST, GGT, total bilirubin (fractionated [direct and indirect], if total bilirubin > 2.0 x ULN), and alkaline phosphatase (fractionated [quantification of isoforms], if alkaline phosphatase > 2.0 x ULN)

 $^{^{\}rm c}$ "Combined" defined as total bilirubin increase to the defined threshold concurrently with ALT/AST increase to the defined threshold

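### Protocol Section 6.5.1 and Table 6-3 give incompatible restart doses after some treatment-related holds, most clearly when LVEF recovers after a mandatory interruption

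*Protocol*

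**What the plan says.** Protocol Section 6.5.1 sets the restart dose by time.

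- Toxicity resolved within 7 days of onset: "treatment may be resumed at the same or a lower dose level at the Investigator's discretion, except for toxicities that require permanent treatment discontinuation".
- Treatment-related interruption: if it lasts "more than 7 but not more than 21 days, study treatment may be resumed but only at a lower dose level". There is one exception: "If the participant is already at the lowest dose level, participant might continue receiving treatment at the same dose level", given clinical benefit and Medical Monitor approval.
- Interruption beyond 21 days: the participant must be discontinued unless an exception is approved. If an adverse event caused the interruption, "study treatment can only be reintroduced at a lower dose level".

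Table 6-3, in the same section, gives event-specific instructions for adverse drug reactions, each labelled Mandatory or Recommendation. For LVEF below 40% it mandates a hold, a cardiology consultation and repeat imaging after 3 weeks, and then: "If improved to > 45%, restart study treatment at the same dose". The next row (LVEF 40% to 45% with a fall of at least 10 points from baseline) has the same structure, with a same-dose restart once LVEF is back within 10 points of baseline. For ocular Grade 2 events the time limit is 14 days: "Upon resolution to ≤ Grade 1 in < 14 days, may consider reintroducing study treatment without dose reduction".

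Section 6.5.1 also bars deviations from mandatory interruptions and reductions. It contains no general sentence on whether the table row or the duration rule prevails when they differ.

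**The concern.** The text and the table cover the same events. For a hold of more than 7 days the text permits only a lower dose, while several rows direct or permit the same dose. Two sites acting in good faith could therefore restart participants with the same event at different doses, and beyond 21 days one text restarts where the other stops unless an exception is approved.

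This bears first on participants, because the LVEF rows concern a cardiac toxicity under Mandatory instructions. It also bears on reporting. The SAP summarizes relative dose intensity and dose reductions (Sections 2.5.1, 2.5.1.3 and 2.5.1.4) and adverse events requiring dose adjustment (Section 2.9.1.2). Those outputs would partly reflect which paragraph a site followed.

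**Working it through.** No sample size or error rate is involved. The check sets the time bands of Section 6.5.1 against the restart instruction in each row.

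**LVEF interruption rows, recovery branch.** Repeat imaging after 3 weeks means 3 × 7 = 21 days.

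- Hold of exactly 21 days: this falls in the band of more than 7 and up to 21 days, so 6.5.1 allows a lower dose only. The table directs the same dose.
- Hold longer than 21 days: 6.5.1 requires discontinuation or, by approved exception, a lower dose only. The table directs the same dose.
- Imaging a few days early: the hold still exceeds 7 days, so the first result applies.
- Participant already at 100 mg once daily, hold of at most 21 days, clinical benefit and approval: both texts allow the same dose. This is the only overlap. If the hold exceeds 21 days there is none, because 6.5.1 demands a lower dose and also bars any dose below 100 mg once daily.
- LVEF not recovered: the table discontinues permanently. No conflict.
- Third LVEF row (fall of less than 10 points): treatment continues. No restart question arises unless LVEF falls further and the rows above take over.

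**Rows that depart from the lower-dose-only rule after 7 days** (not claimed to be exhaustive):

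| Table 6-3 row | Label | Same-dose restart | Time limit in row |
|---|---|---|---|
| LVEF <40%, recovered | Mandatory | directed | none (imaging at 3 weeks) |
| LVEF 40% to ≤45%, fall ≥10 points, recovered | Mandatory | directed | none (imaging at 3 weeks) |
| Diarrhea G2, first episode | Recommendation | directed | none |
| Rash G2, if interrupted | Recommendation | directed | none |
| Ocular G2 | Recommendation | permitted | under 14 days |
| Creatinine G2 | Recommendation | permitted | none |
| Thyroid G3/4 | Mandatory hold | permitted | none |
| Other endocrine G2/3 | Recommendation | permitted | none |
| Skeletal muscle G2/3 | Recommendation | permitted | none |
| QTc G3 with other contributing factors | Mandatory hold | permitted | none |

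Four rows direct the same dose and six permit it, ten in all. In the six permissive rows a site that reduces after more than 7 days satisfies both texts. A site that uses the row's permission breaches 6.5.1. For ocular G2 this covers holds of 8 to 13 days, taking the hold to last as long as the event.

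**Dose at stake.** From Table 6-4, level 0 is 2 × 200 = 400 mg/day, level −1 is 2 × 100 = 200 mg/day and level −2 is 100 mg/day. One level lower halves the daily dose (200/400 = 100/200 = 50%). Against the SAP's planned intensity of 400 mg/day, the days after restart count at 100% or 50% from level 0, and at 50% or 25% from level −1. Section 6.5.1 allows one re-escalation after at least 21 days at the reduced dose without a further dose-modifying event, so the difference may be temporary.

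**Seven-day rule.** Its exception names only toxicities requiring permanent discontinuation. Yet Grade 4 neutropenia, for example, carries "Mandatory: Interrupt study treatment until resolved to ≤ Grade 2, then reduce 1 dose level" whatever the time to resolution. Grade 4 thrombocytopenia, Grade 4 anaemia and febrile neutropenia are also mandatory reductions.

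**Clocks.** The 7-day rule counts from event onset to resolution, and the next rule counts length of interruption. A 10-day toxicity with a 5-day hold meets neither.

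**The case against.** **The specific row overrides the general text.** Many sites would read it so, but the protocol does not say so. Section 6.5.1 presents the tables as a summary of the modifications, and a summary should not reverse its text. Several rows (Grade 3 neutropenia, Grade 3 anaemia, Grade 2 bilirubin) repeat the 7-day split, so its absence elsewhere could be an exemption or an omission. The sentence on mandatory interruptions and reductions does not settle the LVEF case, because a same-dose restart is neither.

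Several stronger readings are tempting, and the documents do not support them.

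- *The LVEF rows can never be followed.* They can for participants who do not recover and in the approved lowest-level case.
- *The table and text conflict equally in the stricter direction.* For the four mandatory-reduction rows, the sentence barring deviations from mandatory reductions already points to the table. The text also allows a lower dose within 7 days, so reducing satisfies both. What remains is an incomplete exception clause.
- *All ten rows force a breach.* Six are only permissive, and diarrhea G2 and rash G2 are Recommendations. The QTc permission is the weakest example, since an event with other contributing causes may not be treatment-related.
- *Either choice is a citable deviation.* The barring sentence covers only mandatory interruptions and reductions.
- *The section contradicts itself at the lowest dose.* It says "a maximum of two consecutive dose level reductions is allowed after which the participant must be discontinued" and elsewhere lets treatment continue at the lowest level. Table 6-4 defines a second reduced level, which could never be given if two reductions alone forced discontinuation. The natural reading is that no third reduction is allowed.
- *The differing clocks are a contradiction.* They leave a gap, which many rows fill with their own resolution rule.
- *First-in-human interruption rates show how often this will arise.* The counts in Section 2.2.3.3.2 cover treatment-related interruptions without regard to duration. The same section reports no heart failure or cardiac dysfunction among 39 patients, which does not exclude later events.

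**Conclusion.** The protocol is wrong as written on a narrow point. For a participant above the lowest dose level whose LVEF recovers under either interruption row, the Mandatory table instruction and the Section 6.5.1 duration rules cannot both be followed. Diarrhea G2 and rash G2 conflict in the same way for holds beyond 7 days, but as Recommendations. Six further rows permit what 6.5.1 does not.

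The size is one dose level, half the daily dose, until any permitted re-escalation. Beyond 21 days the difference is between restart and discontinuation unless an exception is approved. Frequency is unknown, and no effect on response rate by independent review is shown. The case for correction rests on participant safety and on interpretable dose-intensity and dose-reduction summaries.

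The conclusion assumes that the event is treatment-related, as the title of Table 6-3 implies, and that re-imaging takes place at about 3 weeks. It does not depend on which restart dose is clinically right, and none is proposed here.

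**What to change.** In the next amendment:

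1. Reconcile Section 6.5.1 with Table 6-3, including the recovery branch of the two LVEF interruption rows and the other rows listed above.
2. Add one sentence stating whether the event-specific row or the 6.5.1 duration rule governs when they differ.
3. Extend the exception clause of the 7-day rule to refer to the mandatory-reduction rows.
4. As a minor clarification, state which clock each duration rule uses.

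The choice of restart rule is the sponsor's clinical decision. The cost is amendment wording and a clarification letter to sites, with no new data or procedures.
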